243 optimization phase to assess if making changes to meal coverage with the
244 knowledge that Fiasp® is being used can optimize the advantages of the 670G
245 pump with Fiasp® use, and to observe longer term use of Fiasp® in the 670G
246 pump. This will be a 6 week study.

247

248 *Part 1: Randomized cross-over, blinded study which includes assessment of meal*
249 *pharmacodynamics.*

250 Part 1 will be a randomized cross-over blinded study and will also test to see how
251 the 670G pump responds to the introduction of Fiasp® insulin. Subjects enrolled in

252 the study will have a 2 week period of optimization with weekly assessments of their
253 Carelink download before entering the blinded phase of the study. They will use
254 their usual home insulin during the optimization phase. They will then be started
255 on their first blinded insulin (aspart or Fiasp®) which they will use for 2 weeks,
256 before they cross-over to the other insulin. During the second week of each arm we
257 will:

- 258 1) Assess CGM measurements of:
 - 259 a) time in range (70-180 mg/dl)
 - 260 b) percent time <70 mg/dl,
 - 261 c) mean glucose,
 - 262 d) glucose CV,
- 263 2) Pump data for:
 - 264 a) CHO:I ratios at Breakfast, Lunch and Dinner,
 - 265 b) total daily insulin dose,
 - 266 c) total daily basal insulin,
 - 267 d) insulin delivery from MN to 6AM, and 6AM to MN
- 268 3) We will test to see if there is any difference in pharmacodynamics when
269 using Fiasp® in the home environment when they are eating their usual
270 breakfast.
- 271 4) We will also assess their glucose levels following a high fat meal at dinner of
272 at least 30 grams of fat.

273

274 *Part II: Extended Use Observational Study.*

275 This study will consist of 6 weeks of closely monitored home use of the 670G pump
276 with review of their pump and sensor downloads every 2 weeks by clinicians who
277 are experienced in using the 670G pump. The goals of this phase of the study are
278 to:

- 279 1) Assess how Fiasp® changes meal bolusing, i.e. do adjustments need to be
280 made in their carbohydrate to insulin ratios or timing of their boluses when
281 they are using Fiasp® I
- 282 2) Assess how Fiasp® works with the higher fat meals that may occur with
283 dinner, i.e. will the dinner dose need to be divided into early and late boluses
- 284 3) Assess how Fiasp® affects infusion sites under usual care conditions, i.e are
285 there any local reactions to Fiasp®

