494 the evening (unless they are treating hypoglycemia). They will be asked to take a
495 picture of the dinner meal and identify their food and portion sizes. If they have a
496 smart phone (Android or Apple), they may download Calorie Mamma® or Calorie
497 King® to help them in calculating carbohydrates, protein and fat from the meal.
498 They will do this for each of their dinner meals on each of the days they are doing
499 the breakfast study, and for the breakfast meals they are eating each morning as
500 part of the pharmacodynamic testing. They will change their infusion set before
501 dinner prior to the first day of starting a standard breakfast, i.e., if they work from
502 Monday to Friday, this could be done on Sunday.

503

504 They are blinded to the insulin and the insulin dose decisions for these meals is also
505 not under their control since: 1) The overnight insulin delivery is not under their
506 control, 2) The timing of the meal bolus will be the same for all mornings, the dose
507 will be given immediately before eating, 3) Their dose of insulin will be determined
508 by their pump using their preset insulin-to-carbohydrate ratio and they will be eating
509 the same amount of carbohydrates each morning. They also will not be getting a

510 correction dose of insulin in the morning because they are using the closed-loop
511 controller overnight. If they required a correction dose of insulin, we will not use the
512 data from that morning in our data analysis. We will assess during each of these
513 four weeks the time in-range (70-180 mg/dl), mean glucose, CV, and time <70
514 mg/dl.

515

516 At the end of each two week period of blinded insulin use the participants and the
517 health care providers will be given a questionnaire asking them which insulin they
518 thought they were using, and if they had noticed any advantages to disadvantages
519 while they were using this insulin, and whether they would have wanted to make
520 any changes to their insulin delivery settings while using the insulin.

521

522

523 **Part 2: Extended Use Optimization Study**

524

525 To be eligible for Part 2 one of the inclusion criteria will be that the subject is
526 currently using Fiasp® insulin under their usual care. Subjects for Part 1 may
527 participate in part 2, and we will also recruit subjects outside of part 2 who are
528 currently using a 670G pump and taking Fiasp insulin. They will download their

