727 Withdrawal of a subject will be considered for the following reasons: 1) Failure to
728 monitor their sensor and infusion sites on a daily basis; 2) developing >1.0 mmol/L
729 ketones on 2 or more occasions and failing to change their infusion set or a single
730 episode of diabetic ketoacidosis due to an infusion site failure. For subjects who
731 withdraw or who are withdrawn, their data will be used for analysis purposes up until
732 the time of withdrawal.

733

734 **Confidentiality**

735 For security and confidentiality purposes, subjects will be assigned an identifier that
736 will be used instead of their name. De-identified subject information may also be
737 provided to Medtronic Diabetes.

738

739 **Level of Risk**

740 This research proposal in children is consistent with United States Department of
741 Health and Human Services, Protection of Human Subjects, Subpart D, Section
742 46.404 (Research not involving more than minimal risk).

743

744 **Planned Duration of the Entire Study**

745 Planned duration of the entire study will be 6 months.

747 **CHAPTER 6: STATISTICAL CONSIDERATIONS**

748

749 This is a pilot study to determine if there are any clinical issues with using Fiasp® in
750 the 670G hybrid closed-loop system. These studies are not statistically powered.

751

752 In the blinded cross-over studies (Part I) we will use data obtained during the
753 second week of each arm to compare the following measurements using a mixed-
754 effects model accounting for crossover study design of the study with the sequence
755 of treatment nested within the patient:

756

a) time in range (70-180 mg/dl)

757

b) percent time <70 mg/dl,

758

c) mean glucose,

759

d) glucose CV,

760

e) total daily insulin dose,

761

f) total daily basal insulin,

762

g) insulin delivery from MN to 6AM, and 6AM to MN

763

764 We will test to see if there is any difference in pharmacodynamics when using
765 Fiasp® in the home environment when they are eating their usual breakfast.

766

767 Insulin pharmacodynamics following the standard breakfast will be assessed by
768 measuring the peak glucose concentration (C_{max}), time to C_{max} (t_{max}), and estimated
769 average glucose excursions were assessed using sensor glucose values at a time
770 interval of 0 to 180 minutes after breakfast bolus. If a bolus was given between
771 120-180 minutes following the breakfast bolus, CGM values were only used up to

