772 the time of the bolus. The glucose at the time of the breakfast bolus (Time 0) will be
773 set to 0 mg/dL for each meal, and the remaining CGM values were adjusted
774 proportionally to allow analysis of postprandial glucodynamic parameters. We will
775 utilize a mixed-effects model accounting for crossover study design of the study with
776 the sequence of treatment nested within the patient. Breakfast meals are excluded
777 from postprandial analysis if: 1) the rate of change was greater than 0.3mg/dL/min
778 in the 1 hour prior to breakfast, 2) subjects gave a subsequent bolus prior to 120
779 minutes following the breakfast bolus, or 3) subjects deviated from their typical
780 breakfast. Dinner meals will be assessed when there has been no additional food
781 intake after dinner. The duration of insulin delivery to cover the meal will be
782 determined by the time it takes the post prandial glucose to reach 160 mg/dL
783 beyond 1 hour of eating. The peak glucose will also be recorded.

783

784 During the 6 week optimization study (Part II) we will use data obtained during the
785 first two weeks of the study (before data was reviewed and changes made by the
786 investigators) to data obtained during the last two weeks of the 3 month optimization
787 period. We will compare the following measurements using paired t-tests for data
788 with a normal distribution and a Mann-Whitney rank sum test for data that is not
789 normally distributed:

790

a) time in range (70-180 mg/dl)

791

b) percent time <70 mg/dl,

792

c) mean glucose,

- 793 d) glucose CV,
- 794 e) total daily insulin dose,
- 795 f) total daily basal insulin,
- 796 g) insulin delivery form MN to 6AM, and 6AM to MN
- 797 h) CHO:I ratios at breakfast, lunch and dinner
- 798 i) Active insulin time
- 799 j) Number of days between infusion set changes
- 800 k) Erythema (mm) and induration (mm) at infusion sites when they are changed
- 801 l) Average daily insulin, and mean glucose for each day of infusion set wear
- 802 m) Number of episodes of unexplained hyperglycemia in the first month vrs the
- 803 last month
- 804
- 805
- 806
- 807

808 **CHAPTER 7: REFERENCES**

809

- 810 1. Heise T, Hovellmann U, Nosek L, Sassenfeld B, Thomsen KMD, Haahr H.
811 Pharmacokinetic Properties of Fast-acting Insulin Aspart Administered in Different
812 Subcutaneous Injection Regions: Response to the commentary by Nuggehally R. Srinivas.
813 Clinical drug investigation 2017.

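### The high-fat dinner measure has no rule for a further bolus before 160 mg/dL, so corrected dinners get shortened times and the Fiasp-aspart dinner contrast is likely to be attenuated

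*Combined protocol and SAP*

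**What the plan says.** **Dinner (Chapter 6).** The entry condition is "Dinner meals will be assessed when there has been no additional food" intake afterwards. The measure is "determined by the time it takes the post prandial glucose to reach 160 mg/dL", counted "beyond 1 hour of eating. The peak glucose will also be recorded". There is no condition on later insulin, and no model is named for the dinner comparison.

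**Breakfast (Chapter 6).** A breakfast is excluded if "2) subjects gave a subsequent bolus prior to 120" minutes had passed. For a later bolus, given at "120-180 minutes following the breakfast bolus, CGM values were only used up to" the time of that bolus.

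**Meal-test procedure (Chapter 3, Part 1).** The argument that dosing is outside the participant's control rests on overnight delivery and on mornings: "control, 2) The timing of the meal bolus will be the same for all mornings, the dose" being given just before eating, with the same carbohydrate each day. A morning that needed a correction dose is not analysed. Nothing comparable is said about the evening.

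**Later insulin at dinner is foreseeable.** The test dinner must contain at least 30 g of fat. The risk section in Chapter 4 expects that glucose may stay high for a long time after such a meal. Chapter 3 refers to correction boluses for unexplained hyperglycemia. Part II goal 2 in section 1.4 asks about higher-fat meals at "dinner, i.e. will the dinner dose need to be divided into early and late boluses".

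**The concern.** The dinner measure is meant to show how long the meal keeps glucose up under each insulin. A further bolus given because glucose is still high brings the 160 mg/dL crossing forward. The plan then records a shorter time for a dinner whose first dose did not suffice. Corrections should be commoner on whichever insulin leaves glucose higher, so the shortening falls more heavily on that arm and pulls the two arms together.

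This is the only Chapter 6 analysis specific to the high-fat dinner, which section 1.4 lists among the Part 1 assessments. With up to 20 subjects and three dinners per insulin, there are at most 60 dinners per arm (20 × 3), so a modest number of corrected dinners can move the result.

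**Working it through.** The plan gives no effect size, SD or correction rate for dinner, so there is no stated figure to reproduce. Apart from the 160 mg/dL threshold, every input below is an assumption, used to show direction and rough size.

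**1. One dinner, with and without a correction.** Time to 160 = time of peak + (peak − 160) / fall rate. Assume a peak of 240 mg/dL at 2.5 h and a fall of 20 mg/dL/h.
- No correction: 2.5 + 80/20 = 6.5 h.
- Correction at 3 h, adding 30 mg/dL/h from 3.5 h: glucose at 3.5 h is 240 − 20 = 220, so the crossing is at 3.5 + 60/50 = 4.7 h.
- Shortening: 6.5 − 4.7 = 1.8 h. It runs from 0.67 h (fall 30, added 20) to 3.15 h (fall 15, added 40).

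**2. Two insulins, single meals.** Insulin A peaks at 240 and insulin B at 210, both at 90 min, and both fall 0.4 mg/dL/min.
- Uncorrected: A reaches 160 at 90 + 80/0.4 = 290 min, B at 90 + 50/0.4 = 215 min.
- A is then corrected at 120, 150, 180 or 240 min, with a 20 min lag and an extra fall of 0.25, 0.5, 0.8 or 1.2 mg/dL/min. This gives 16 cases.
- A is recorded at 178 to 279 min, always earlier than its own 290 min. It comes out earlier than B's 215 min in 5 of the 16. For example, a correction at 120 min with extra fall 0.5 gives 140 + 60/0.9 ≈ 207 min.

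**3. Difference in mean times, same correction behaviour on both insulins.** Mean peak is 215 against 235 mg/dL (SD 35), fall 0.4 mg/dL/min (SD 0.1). A correction may be given at 150 min if glucose is above 200. The ranges are over an extra fall of 0.5 or 1.0 mg/dL/min.

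| High dinners corrected | Dinners corrected, better vs worse insulin | True gap | Recorded gap | Gap if corrected dinners are dropped |
|---|---|---|---|---|
| None | 0% vs 0% | 53 min | 53 min | 53 min |
| Half | 20% vs 31% | about 53 min | 36-39 min | 49-50 min |
| All | 40% vs 62% | about 53 min | 18-26 min | 17 min |

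The mean order did not reverse in any run, including runs with peak differences of 10 and 30 mg/dL. The last column shows that exclusion alone is not a safe remedy.

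**4. A second simulation with other assumptions.** Mean peak is 225 against 213 (SD 35), fall 20 mg/dL/h (SD 6). A correction adds 30 mg/dL/h from 0.75 h after the peak, in dinners peaking above 220. The true difference is −0.66 h.
- Equal correction rates of 25, 50 and 75%: recorded −0.55, −0.45 and −0.35 h. The loss runs from 0.11/0.66 = 17% to 0.31/0.66 = 47%.
- Rates of 75% on the slower insulin and 25% on the faster: +0.19 h, a reversal.
- A rebuild with a different truncation of the fall rates (true −0.63 h) gave about −0.20 h with all such dinners corrected on both insulins and −0.16 h at 60% against 40%. Neither reverses.

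**The case against.** **A reader might infer that the poorer insulin will be recorded as clearing the meal sooner.** The documents do not support that as a general statement. Shortening is certain only against the same dinner left uncorrected. Reversal of the means in step 4 needs participants to correct three times as often on one insulin among dinners that already peak above 220. Participants and investigators are blinded, and the higher peaks already give the slower insulin more such dinners (about 56% against 42%). Nothing in the documents supports the further threefold gap. This objection stands.

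**A reader might infer that the evidence for Part II goal 2 is lost.** It is not. Time to 160 mg/dL is not among the Part II comparisons, and the bolus records stay in the CareLink uploads. They are simply not linked to the dinner score.

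**A reader might credit the authors with a stated reason for the breakfast rules.** Chapter 6 gives none. That they keep later insulin out of the meal response is an inference, though a natural one.

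**Time to 160 under the whole system is a legitimate question in a closed-loop pilot.** The pump also adjusts basal delivery after dinner, and that is not the meal dose either. This stands in part. It is a reason to report automatic basal units and to keep an analysis of all dinners as recorded. It does not explain why a user bolus is handled at breakfast and not at dinner.

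**The study is an unpowered pilot with many measures.** Peak glucose, total and basal insulin, and delivery from midnight to 6 AM are also compared by arm, so extra insulin is partly visible. This limits the weight of the point but does not tie the insulin to a dinner.

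**Conclusion.** The point holds as an omission with a predictable direction. Following Chapter 6 as written shortens the recorded time for any dinner in which a further bolus takes effect before 160 mg/dL. The Fiasp-aspart dinner contrast is therefore likely to be attenuated if the insulin that covers the meal less well triggers more corrections. On the assumed values, the loss in mean times runs from about a sixth to about two thirds of the true gap (17% in step 4; 35/53 = 66% in step 3). Reversal is possible for single meals, and for means only if correction rates differ strongly between insulins.

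All sizes depend on assumed peaks, fall rates, correction effects and correction frequencies. If corrections after test dinners prove rare, the effect is small. The plan should be changed, but in an unpowered pilot this does not threaten the study as a whole.

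**What to change.** Add a dinner rule to Chapter 6.

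- **(a) Scoring.** Do not score a dinner with a further user bolus before 160 mg/dL by its post-bolus crossing time. Record it as not reached without further insulin, for example by worst rank. Worst rank is one defensible choice among several, so add two sensitivity analyses: one that censors at the bolus, stating that this censoring is informative, and one that uses all dinners as recorded.
- **(b) Reporting.** From the CareLink uploads, report by insulin the share of test dinners with a later bolus, and the correction plus automatic basal units in a fixed post-dinner window.
- **(c) Peak.** Keep the full peak as recorded, flagged by whether a bolus preceded it. Do not cut it at the bolus: that can only lower the peak, only in corrected dinners, and so would favour the insulin that needed the correction.

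The cost is some SAP wording, slightly more programming, and a rank-based or composite summary that is less direct to read than a mean time. The pump data are already uploaded weekly in Part 1. No change to patient care is involved.

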- 286 4) Assess if Fiasp® becomes less effective over the life an infusion set (are sets
287 changed more frequently)
- 288 5) Assess how the 670G performs when Fiasp® is used:
 - 289 a. Do insulin-to-carbohydrate ratios need to be modified
 - 290 b. Does duration of insulin action need to be modified
 - 291 c. Is more or less basal insulin delivered
 - 292 d. Does the total daily dose change
 - 293 e. Does the performance of the 670G change overnight (MN to 6AM)
294 and during the day (6AM to MN) in terms of time in range, mean
295 glucose and % of readings <70 mg/dL.

296

297 will include both males and females and an enrollment goal will be to achieve an

298 approximately equal sex distribution. Their total daily insulin dose should be at least
299 0.3 units/kg/day and they should be eating at least 60 grams of carbohydrate each
300 day.

301

302 **General Considerations**

303 The study is being conducted in compliance with the policies described in the study
304 policies document, with the ethical principles that have their origin in the Declaration
305 of Helsinki, with the protocol described herein, and with the standards of Good
306 Clinical Practice.

307

308 **CHAPTER 2: SUBJECT ENROLLMENT AND STUDY INITIATION**

309

310 **Study Enrollment and Duration**

311 Part 1: Randomized cross-over, blinded study with assessment of meal
312 pharmacodynamics: up to 20 subjects will be studied and the studies for each
313 subject will last 6 weeks.

314 Part 2: Long term use of Fiasp®. We will recruit up to 20 subjects who are using
315 Fiasp® insulin, they are not excluded if they were in Part 1, in fact subjects in part 1
316 will be encouraged to continue into part 2 of the study. Duration is up to 6 weeks, or
317 until subject decides to stop using Fiasp®.

318

319 **Eligibility and Exclusion Criteria**

320

321 **Eligibility Criteria**

322 To be eligible for the study, a subject must meet the following criteria:

- 323 1. Clinical diagnosis of type 1 diabetes and using 670G pump for at least 1
324 month, and willing to have the 670G pump downloaded into a Carelink
325 Clinical research database.
- 326 2. The diagnosis of type 1 diabetes is based on the investigator's judgment; C-
327 peptide level and antibody determinations are not needed.
- 328 3. Age ≥18 years
- 329 4. Using Novolog or Fiasp® insulin at time of enrollment
- 330 5. Willing to use Fiasp® insulin
- 331 6. Total daily insulin dose is at least 0.3 units/kg/day

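### Part 2 is given as both 6 weeks and 3 months; at 6 weeks the two months of item (m) share half their days, and non-normal paired data get an unpaired test

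*Combined protocol and SAP*

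**What the plan says.** The Part II paragraph of Chapter 6 (Statistical Considerations) opens with "During the 6 week optimization study (Part II) we will use data obtained during the" and sets the baseline as the "first two weeks of the study (before data was reviewed and changes made by the" investigators. The same sentence takes the follow-up from "investigators) to data obtained during the last two weeks of the 3 month optimization" period.

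Thirteen items, (a) to (m), are listed for comparison. Item (m) has windows of its own: "Number of episodes of unexplained hyperglycemia in the first month vrs the" last month. Month is not defined in days. Normally distributed data get a paired t-test. The rest is described as data "with a normal distribution and a Mann-Whitney rank sum test for data that is not" normally distributed.

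Elsewhere the length of Part 2 appears as follows:

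- Section 1.4, synopsis: "pump. This will be a 6 week study".
- Section 1.4, Part II: "This study will consist of 6 weeks of closely monitored home use of the 670G pump".
- Chapter 2, Study Enrollment and Duration: "will be encouraged to continue into part 2 of the study. Duration is up to 6 weeks, or" until the subject stops Fiasp.
- Chapter 2, HbA1c: measurements at the start and end of an observational study described as lasting 3 months.

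**The concern.** One sentence gives two lengths for the same study part, and the choice between them decides which data enter the analysis. At 3 months, the windows can be formed as written. At 6 weeks, the follow-up window as worded does not exist, and item (m) compares two periods that run into each other. Changing 3 month to 6 week in that sentence would rescue the two-week items but leave item (m) overlapping.

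Item (m) is the only Part II item that counts unexplained hyperglycemia, which also features in the infusion-set replacement criteria in Chapter 3. Finding clinical issues of this kind is the stated purpose of the pilot.

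The choice of test is a second and separate matter. Every Part II comparison is within subject. The plan respects this for normal data and drops it for non-normal data. Counts of infrequent episodes are likely to fall in the second group.

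**Working it through.** **Inputs.** Part 2 length T: 42 days (section 1.4, Chapter 2 enrollment, opening of the Chapter 6 sentence) or 84 to 91 days (HbA1c section, end of the Chapter 6 sentence). Two-week windows: 14 days. Month length L: not defined, so 28, 30 and 31 days are tried.

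**Two-week windows.** The last 14 days are days T-13 to T.

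- T = 42: days 29-42.
- T = 84: days 71-84.
- T = 90: days 77-90.

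A window at the end of 3 months starts on day 71 at the earliest, so a subject followed for 42 days contributes nothing to it. Days 1-14 and 29-42 do not overlap. Read within 6 weeks, the two-week items are therefore sound.

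**Item (m).** First month = days 1 to L; last month = days T-L+1 to T; shared days = max(0, 2L - T).

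| T | L | Shared days | Share of each month |
|---|---|---|---|
| 42 | 28 | 56 - 42 = 14 (days 15-28) | 50% |
| 42 | 30 | 60 - 42 = 18 (days 13-30) | 60% |
| 42 | 31 | 62 - 42 = 20 (days 12-31) | 65% |
| 84 to 91 | 28 to 31 | 0 | 0% |

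The enrollment section lets a subject stop before 6 weeks, which widens the overlap. For example, stopping at day 28 with L = 28 gives 56 - 28 = 28 shared days, so the two months are identical.

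**Effect on a paired difference.** Let A, B and C be a subject's counts in days 1-14, 15-28 and 29-42. With L = 28 the difference is (A + B) - (B + C) = A - C. The shared block cancels, and the result contrasts days 1-14 with days 29-42 under a month-to-month label. With L = 30, only days 1-12 and 31-42 remain.

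**Effect on the Mann-Whitney test.** This test ranks the totals A + B and B + C as if they came from different subjects. B does not cancel. It adds to both totals and makes them more alike, on top of the ordinary within-subject correlation that the test already ignores. With positive correlation the test rejects too rarely.

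A simulation sizes the joint effect of test and windows. Its inputs are assumptions, because the documents give no episode rate: 20 subjects (the planned maximum), Poisson counts averaging 2 or 4 per two weeks, gamma variation between subjects with shape 1 to 5, a 50% fall with half of it reached in days 15-28, and two-sided 0.05.

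- Mann-Whitney on overlapping 28-day months detects the fall in 0.3-28% of trials.
- Signed-rank on days 1-14 versus 29-42 detects it in 61-93%.
- With no change, the overlapping Mann-Whitney rejects in about 0% of trials.

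**Can the documents settle T?**

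- *Payment (Chapter 5, Subject Compensation).* Part 2 pays $50 per visit and $20 per two-weekly upload, to a maximum of $160. Solving 50v + 20u = 160 with at least one visit gives only v = 2, u = 3: $100 + $60. Three two-weekly uploads fit 6 weeks. Six uploads cost $120 and leave $40, which is not a whole visit. This leans toward 6 weeks.
- *Total duration (Chapter 5): 6 months, about 26 weeks.* At the recruitment goal of 4 per week, 20 subjects take 5 weeks, and Part 1 takes 6. Then 5 + 6 + 6 = 17 weeks, or 5 + 6 + 12 to 13 = 23 to 24 weeks. Both fit.

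**The case against.** The strongest reply is that the overlap does little harm to the planned result. Item (m) is a number of episodes, and with 28-day months a paired difference is exactly what disjoint windows would give. That stands for the paired t-test. It does not cover the Mann-Whitney route, where nothing cancels, nor 30-day months, nor the misleading label.

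It can also be said that the monthly comparison fits a 3-month design, so item (m) merely follows from one unreconciled duration. That is fair. It is also why correcting the duration alone is not enough if the answer is 6 weeks.

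Three stronger readings are tempting and not supported:

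- *The overlap shrinks the reported relative change by a known percentage.* The plan reports no rate, ratio or relative change for item (m), and any such percentage would rest on an invented size and timing of the fall.
- *Item (m) is spoiled because much of its first month follows the first data review.* That would be equally true in a 3-month Part 2, where the windows are disjoint. The item states its own windows, and the pre-review baseline is attached to the two-week comparison.
- *Part 2 certainly lasts 6 weeks, so the follow-up data cannot exist.* The payment cap only leans that way. Chapter 3 asks subjects to keep using Fiasp while they see benefit, with two-weekly downloads. It sets no 3-month endpoint, but it does not exclude later data either.

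**Conclusion.** The point holds. The length of Part 2 is contradictory in the current text, and within a single sentence of the analysis plan. If it is 6 weeks, the follow-up window as written is empty and the two months of item (m) share 14 of 28 days, or 18 of 30. If it is 3 months, neither problem arises. The two-week items have a natural reading within 6 weeks, so for them this is a conflict of wording.

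Independently of the duration, the Mann-Whitney test is the wrong companion to a paired t-test. With positively correlated windows it errs toward missing changes, not toward false findings. The simulated detection figures rest on assumed rates, and they change test and windows together, so they show direction and rough order only.

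The consequence is limited: these are exploratory comparisons in a pilot that the protocol says is not statistically powered. It should be fixed, but it does not threaten the study.

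**What to change.** 1. Reconcile the Part 2 duration across section 1.4, Chapter 2 (enrollment and HbA1c) and Chapter 6, including when the final HbA1c is taken.
2. Write every Part II window as day numbers, and define the last two weeks for subjects who stop early.
3. If 6 weeks, compare days 1-14 with days 29-42 for item (m) too. If 3 months, state the last-14-day window and the month length in days; item (m) can then keep its monthly windows.
4. Replace the Mann-Whitney test with the Wilcoxon signed-rank test for non-normal paired data.

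The cost is wording only, since the two-weekly downloads are already planned. The one downside arises at 6 weeks: item (m) would use 14-day windows, half of a 28-day month, so fewer episodes enter each period's count. With 28-day months the paired difference loses nothing, because the shared days cancel anyway.
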